STATISTICAL ANALYSIS

The data to be collected for the study will be recorded using SPSS 22 program and analyzed in the same program. Frequency, percentage, mean value, standard deviation, maximum and minimum (min-max) values will be used for descriptive statistics, Pearson Chi square test will be applied for statistical analysis of categorical data and Fisher's Exact Test will be applied for values below five in four-sided tables. The conformity of quantitative data to normal distribution will be tested with Kolmogorov-Smirnov and Shapiro Wilk tests. For statistical analysis of quantitative data in independent groups, Unpaired t test and One-Way Anova test (post hoc Tukey test) will be used for data conforming to normal distribution, Mann-Whitney U, Kruskall-Wallis test will be used for data not conforming to normal distribution and Pearson Correlation coefficient will be used to show the relationship between variables. Statistical significance of the difference was accepted as $p < 0.05$.

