
RESEARCH PROTOCOL

lumen tubes are cost effective, their superiority over other techniques has not been demonstrated because their use has not yet become widespread. Another aim of the study is to compare the cost effects of these three methods.

Using the studies in the literature, the total number of patients for three groups was found to be 93 by using G-power to calculate the sample size and taking the effect size as 0.33 at a 95% confidence level and 80% power.

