In Kayseri City Hospital, ASA I-III patients aged 18-84 who are planned to undergo surgery with single lung ventilation between December 2024 and May 2025 will be included in the study after obtaining their informed consent. In our hospital, video double lumen tube verification techniques, and auscultation and fiberoptic bronchoscopy are routinely used for conventional double lumen tubes. Patients are blinded in terms of the method to be applied, and since the anesthesiologist who will perform the intubation procedure is the person who performs the method, blinding cannot be performed. Anesthesiologists who perform the intubation procedure will not have any information about the study. They will use the method they prefer. Patient randomization will be done in this way. In the study, volunteers were blinded because they did not know which intubation method would be used, while blinding could not be done for the anesthesiologist who would perform the intubation. Due to the advantages mentioned above, a left tube will be used in all patients. Tube sizes will be determined according to the height and gender of the patients. Group I will be divided into three groups randomly as patients whose tube location will be confirmed by auscultation, Group II patients whose tube location will be confirmed by using fiberoptic bronchoscopy, and Group III patients whose tube location will be confirmed by using a video-guided double-lumen intubation tube. After the patients are taken to the operating room, routine monitoring will be applied and vascular access will be established with an 18G intravenous catheter. After preoxygenation with 100% O₂ for 2 minutes, anesthesia induction will be applied with 2-3 mg/kg propofol, 1-2 mcg/kg fentanyl, and 0.6mg/kg rocuronium. They will be ventilated with 100% oxygen until neuromuscular blockade occurs for at least 2 minutes. The intubation duration will be started after the vocal cords are visualized with the laryngoscope and will be taken as the time until end tidal CO₂ is seen on the monitor. Intubation verification time was planned for Group I as the time when bilateral respiratory sounds are heard while both cuffs are inflated, then the tracheal lumen is clamped and no respiratory sounds are heard on the right, respiratory sounds are heard on the left and then the bronchial lumen is clamped and no respiratory sounds are heard in the left lung, and respiratory sounds are confirmed to be heard in the right lung. For Group II, it was planned to be taken as the time when the fiberoptic bronchoscope is first entered into the tracheal lumen and the carina and bronchial blue-colored cuff is seen to be inflated without herniation in the left bronchus and then entered through the left bronchial lumen and it is seen that the tube is not advanced too much. III. In the group, it was planned to be taken as the time when the bronchial lumen of the video double lumen tube entered the left bronchus and the blue cuff was inflated. After the patients were given the lateral decubitus position with the lung to be operated on top, the tube location for each group was confirmed again and the time was recorded. Anesthesia maintenance will be provided using 1 MAC sevoflurane. The number of intubation attempts in the 3 groups, the duration of intubation, the duration of tube location verification, the quality of lung collapse, the need for fiberoptic bronchoscopy, the duration of fiberoptic bronchoscopy, the number of tube dislocations, and the duration of dislocation correction will be monitored. After extubation, the patients will be taken to the recovery room. In the recovery room, the patients will be questioned about the presence of sore throat and hoarseness. The methods used in the patients will be compared in terms of cost according to the type of tube and the use of fiberoptic. The data to be collected for the study will be recorded using the SPSS 22 program and analyzed in the same program. Frequency, percentage, mean value, standard deviation, maximum and minimum (min-max) values will be used for descriptive statistics, Pearson Chi-square test will be applied for statistical analysis of categorical data and Fisher's Exact Test will be applied for values below five in four-sided tables.

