
RESEARCH PROTOCOL

The conformity of quantitative data to normal distribution will be tested with the Kolmogorov-Smirnov and Shapiro Wilk tests. For statistical analysis of quantitative data in independent groups, Unpaired t test and One-Way Anova test (post hoc Tukey test) will be used for data conforming to normal distribution, Mann-Whitney U, Kruskall-Wallis test and Pearson Correlation coefficient will be used to show the relationship between variables for data not conforming to normal distribution. Statistical significance of the difference was accepted as p<0.05.

SOURCES:

1. Mehrotra, M. and A. Jain, Single-Lung Ventilation, in StatPearls [Internet]. 2023, StatPearls Publishing.
2. Hickey, S.M. and A.O.J.T.I.S.P. Giwa, Mechanical ventilation. 2020.
3. Morgan, G. and M.J.K.A. Mikhail, MurrayMJ. 2002: p. 1040-2.
4. Campos JH. Current techniques for perioperative lung isolation in adults. *Anesthesiology*. 2002; 97:1295–1301.
5. Liu, S., Y. Mao, P. Qiu, et al., Airway rupture caused by double-lumen tubes: A review of 187 cases. 2020. 131(5): p. 1485-1490.
6. Campos JH. Which device should be considered the best for lung isolation: double-lumen endotracheal tube versus bronchial blockers. *Current Opinion in Anesthesiology*2007
8. The Video Double-Lumen Endobronchial Tube: Is the Benefit Worth the Cost? *Journal of Cardiothoracic and Vascular Anesthesia* 32 (2018) 275–276

RESPONSIBLE RESEARCHER: Doc. Dr. [name]

ASSISTANT RESEARCHER: [name] [name]

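### Protocol ties Pearson correlation to non-normal data, the SAP uses it without condition, and neither names a rank correlation (minor)

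*SAP*

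**What the plan says.** **Correlation.** The last statistical paragraph of the protocol puts the coefficient in the clause on non-normal data: "Pearson Correlation coefficient will be used to show the relationship between variables for data not conforming to normal distribution". In the SAP, Statistical Analysis, the non-normality condition attaches to the Mann-Whitney and Kruskal-Wallis tests, and the coefficient stands alone: "Pearson Correlation coefficient will be used to show the relationship between variables". Neither document names Spearman or another rank correlation. Neither says which variables will be correlated.

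**Categorical data (side note).** The SAP's default is "Pearson Chi square test will be applied for statistical analysis of categorical data". The exception is "Exact Test will be applied for values below five in four-sided tables", and the protocol has the same exception. Four-sided is read here as 2x2. In the recovery room "the patients will be questioned about the presence of sore throat and hoarseness", so each symptom compared over three groups gives a 3x2 table.

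**Size and allocation.** On size, "the total number of patients for three groups was found to be 93"; no group sizes or ratio are given. On allocation, the protocol says of the anesthesiologists "They will use the method they prefer", and also "Group I will be divided into three groups randomly".

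**The concern.** Read literally, the protocol reserves Pearson correlation for the data to which it is least suited, while the SAP applies it to everything. An analyst cannot follow both. Both documents already accept that non-normal data call for rank methods when groups are compared, so the correlation rule is out of step with the rest of the plan. The protocol collects intubation, verification and correction times, which are often right-skewed, counts of attempts and dislocations that take few values, and a quality-of-collapse measure that may be graded. With such variables Pearson is sensitive to a few long times and can miss a monotone association. If the choice of coefficient stays open, it could also be made after both results have been seen.

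The Fisher restriction raises a similar question: the plan treats small counts as needing an exact test, yet gives none for the three-group table.

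**Working it through.** **1. The plan's own figure.** One-way ANOVA, three groups, effect size f = 0.33, alpha 0.05: noncentrality = 93 x 0.33^2 = 10.13, and power is 0.807 at N = 93 (0.793 at N = 90). The stated 93 is reproduced, and nothing below changes it.

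**2. The two correlation sentences side by side.**
- Protocol: rank tests and Pearson share one clause, which ends in the non-normality condition.
- SAP: the same elements in a different order; the condition closes after the rank tests, and Pearson has none.
- The documents therefore disagree for normal data (Pearson under the SAP, no coefficient under a literal reading of the protocol). They agree on Pearson for non-normal data, which is the less suitable choice.

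**3. What Pearson can cost (all settings assumed).** A simulation of lognormal pairs with n = 93 gave power of 50% to 73% for Pearson and 79% for Spearman. The arithmetic for one such setting, with both variables lognormal and a correlation of 0.3 on the log scale, shows why:
- Critical |r| at n = 93, two-sided 5%: 1.986 / sqrt(91 + 1.986^2) = 0.204.
- Pearson's population value with log SD 1: (e^0.3 - 1)/(e - 1) = 0.350/1.718 = 0.204. This equals the critical value, so power is about 50%.
- With log SD 0.5: (e^0.075 - 1)/(e^0.25 - 1) = 0.0779/0.2840 = 0.274.
- Spearman's population value: (6/pi) x arcsin(0.15) = 0.288, whatever the log SD.
- A check with 20,000 simulated samples in this setting gave 51% (log SD 1) and 74% (log SD 0.5) for Pearson, and 80% for Spearman. With no association, both rejected in about 5% of samples. With normal data, Pearson was better (84% against 80%).

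**4. Side note: chi-square in sparse 3x2 tables** (full enumeration; event rates and unequal splits are assumed).
- With 31 per group, the expected number of events per group is T/3, which is below 5 when total events T are fewer than 15.
- Type I error of chi-square with 31 per group: 0.6%, 2.1%, 3.2%, 3.6%, 4.1%, 5.0%, 5.0% at rates 1%, 2%, 3%, 5%, 10%, 20%, 30%.
- Single table 3/0/0: chi-square = 6/1 + 6/30 = 6.2, p = e^-3.1 = 0.045. Conditional exact p = 3 x 4,495/129,766 = 0.104. Unconditional exact p = 0.049.
- One event in the whole trial, in a group of k: chi-square = (93/92)(93/k - 1). For k = 13 this is 6.22, p = 0.045, against a conditional exact p of 13/93 = 0.140 if that group is the unique smallest. For k = 14 it is 5.70, p = 0.058.

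Type I error of chi-square, unequal groups:

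| Split | 1% | 2% | 3% | 5% | 10% |
|---|---|---|---|---|---|
| 20/60/13 | 6.6% | 7.2% | 6.5% | 5.2% | 4.7% |
| 67/13/13 | 11.5% | 11.1% | 8.9% | 5.8% | 4.2% |

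Over these rates, with at least 14 per group the maximum is 5.6% (65/14/14, rate 5%), and with at least 20 per group it is 5.0%.

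Power with 31 per group, Fisher-Freeman-Halton when any expected count is below 5, against chi-square throughout:
- 10%/1%/1%: 28% against 40%
- 20%/5%/5%: 44% against 47%
- 30%/10%/10%: 54% against 56%

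**The case against.** **On correlation.** The protocol sentence is a run-on. The SAP has nearly the same words in a clearer order, so the intended meaning is probably the SAP's and the mismatch is close to editorial. No correlation hypothesis is stated, so no planned comparison depends on it. Pearson also kept its error rate in the simulated setting, and with normal data it is the better choice. All of this is fair and sets the grade at minor. What stands is that the two texts differ and that, even on the SAP's reading, non-normal and ordinal variables are left without a rank coefficient, contrary to the plan's own practice for group comparisons.

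**On Fisher's test.** A reader might infer that confining it to 2x2 tables makes the three-group symptom comparisons invalid. The documents do not support this. With equal groups chi-square holds its level, and in the 3/0/0 table the unconditional exact p falls on the same side of 0.05 as chi-square. A reader might also infer from the allocation wording that one group will be very small. That is possible but not established: the protocol describes both choice by preference and random division, and fixes no group sizes. The allocation contradiction is a separate and weightier matter and should not lend weight to this one. Pairwise 2x2 tables are covered by the plan as written.

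**Conclusion.** The correlation rule is inconsistent between the documents and incomplete in both. This is a minor point. It touches only exploratory associations, and neither the sample size nor any group comparison changes. The size of the loss (79% power falling to between 50% and 73%) rests on assumed lognormal data. It shrinks with milder skew and reverses for normal data, for which the proposed rule keeps Pearson.

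The Fisher restriction is a choice to settle before analysis and does not have to be corrected. Chi-square inflation needs a group of about 13 together with event rates of about 1% to 3%, and the documents give neither group sizes nor rates. The symptoms concerned are recovery-room outcomes, not the tube-positioning outcomes that the primary purpose centres on. The exact alternative is conservative when events are rare: with 31 per group its type I error is 0.04% to 1.9% at rates of 1% to 5%, and three or fewer events can never reach p < 0.05.

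**What to change.** In both documents, replace the correlation wording with: *Pearson correlation is used for normally distributed variables, Spearman correlation for non-normal or ordinal variables.* It would help to add that a pair counts as non-normal if either variable does. The cost is one sentence per document, with no change to sample size or data collection.

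Optional, for the side note: state before analysis which test applies to tables larger than 2x2 with small counts, and whether small means expected or observed. Keeping chi-square is defensible if the groups turn out roughly equal. Naming Fisher-Freeman-Halton protects against a very small group, costs the power shown above, and needs a check that the SPSS 22 installation computes it for tables larger than 2x2.

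### ANOVA and Tukey pool one variance across the groups, so the 5% error rate is not assured if group sizes and spreads both differ; Welch and Games-Howell would hold it at almost no cost

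*SAP*

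**What the plan says.** The SAP (Statistical Analysis) and the statistics paragraph at the end of the protocol give the same rule for quantitative outcomes. The only assumption checked is normality: "The conformity of quantitative data to normal distribution will be tested with Kolmogorov-Smirnov and Shapiro Wilk tests". For data that pass, "Unpaired t test and One-Way Anova test (post hoc Tukey test) will be used for data conforming to normal distribution". Data that fail go to Mann-Whitney U or Kruskal-Wallis. Neither document names a check of equal variance or a method that allows unequal variance.

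On group sizes, the protocol's sample-size paragraph gives only a total: "the total number of patients for three groups was found to be 93". The methods paragraph says of the anesthesiologists: "They will use the method they prefer. Patient randomization will be done in this way". A few sentences later it says "Group I will be divided into three groups randomly". No allocation ratio, block or per-group number appears.

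The same paragraph defines verification time separately for each group: auscultation with sequential clamping in Group I, bronchoscopy through both lumens in Group II, and the view from the video tube in Group III. No standard deviation is given for any outcome.

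**The concern.** Classical ANOVA and Tukey estimate one common variance from all three groups. With equal group sizes the error rate is fairly robust when that assumption fails. With unequal sizes it is not. If the small group is the variable one, the pooled variance is too small for the comparison and false positives rise. If the large group is the variable one, the test becomes too strict.

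This plan secures neither condition. Operator preference does nothing to balance the sizes, and three different verification procedures give no particular reason to expect equal spread in the times.

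The protocol's aim is to find the method that verifies tube position in the shortest time. For any duration that passes the normality check, that claim rests on these tests. A wrong variance can produce a false claim of a faster method, or hide a real difference between two methods.

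**Working it through.** **Inputs.** From the documents: N=93, three groups, effect size 0.33 (read as Cohen's f), significance level 0.05, power 80%. Assumed, because the documents give none: group sizes, SD ratios, and normal data (the branch at issue).

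**1. The plan's own figure.** The protocol reports "taking the effect size as 0.33 at a 95% confidence level and 80% power". For one-way ANOVA the noncentrality is λ = N·f² = 93 × 0.33² = 10.13, with 2 and 90 degrees of freedom. Power is 80.2% at N=92 and 80.7% at N=93. The smallest total divisible by three that reaches 80% is 93, or 31 per group. The figure reproduces.

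**2. Why group sizes matter.** With equal means, group sizes nᵢ and variances σᵢ²:

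- E(MS between) = Σ(1 − nᵢ/N)σᵢ² / 2
- E(MS within) = Σ(nᵢ − 1)σᵢ² / (N − 3)

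ANOVA behaves well when their ratio is 1. With 31 per group both equal the mean of the three variances, so the ratio is 1 whatever the SDs. With unequal groups it is not:

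- 45/30/18, SD 1:1.5:2: between = (48/93×1 + 63/93×2.25 + 75/93×4)/2 = 2.633; within = (44×1 + 29×2.25 + 17×4)/90 = 1.969; ratio 1.34.
- 50/30/13, SD 1:2:3: 5.457/3.033 = 1.80.
- 13/30/50, SD 1:2:3: 3.866/6.322 = 0.61.

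**3. Error rate by simulation.** No true difference, nominal 5%, 100,000 runs per row. Tukey and Games-Howell columns are the chance of any false pairwise finding.

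| Group sizes | SDs | ANOVA | Tukey | Welch | Games-Howell |
|---|---|---|---|---|---|
| 31/31/31 | 1:1.5:2 | 5.6% | 5.6% | 5.0% | 5.0% |
| 31/31/31 | 1:1:3 | 7.3% | 6.7% | 5.0% | 4.6% |
| 35/31/27 | 1:1.2:1.4 | 5.8% | 5.9% | 5.0% | 5.0% |
| 35/31/27 | 1:2:3 | 8.0% | 8.0% | 5.0% | 4.8% |
| 36/31/26 | 1:1.5:2 | 7.2% | 7.3% | 5.0% | 4.9% |
| 45/30/18 | 1:1.5:2 | 10.8% | 11.0% | 4.9% | 4.8% |
| 50/30/13 | 1:2:3 | 18.5% | 18.8% | 5.1% | 4.8% |
| 45/30/18 | 2:1.5:1 | 2.7% | 2.5% | 5.1% | 5.1% |
| 13/30/50 | 1:2:3 | 1.6% | 1.6% | 4.9% | 4.9% |

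A wider grid (sizes as uneven as 55/25/13, SD ratios up to 3) gave 0.6% to 23.4% for ANOVA and 4.7% to 5.2% for Welch.

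**4. Power of the pairwise step with equal groups.** Take 31 per group, SDs 1:1:2, and a true difference of 0.8 between the two steadier groups.

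- True standard error of that difference: √(2/31) = 0.254.
- Tukey's pooled SD: √((1+1+4)/3) = 1.414. The studentized range quantile for 3 groups and 90 df is 3.370, so the observed difference must exceed (3.370/√2) × 1.414 × 0.254 = 0.856. Power ≈ Φ((0.8 − 0.856)/0.254) = Φ(−0.22) = 41%.
- Games-Howell uses only these two groups' variances (60 df, quantile 3.399): (3.399/√2) × 0.254 = 0.610. Power ≈ Φ((0.8 − 0.610)/0.254) = Φ(0.75) = 77%.

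Simulation gives 42% and 77%.

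**5. The rank-test branch.** Kruskal-Wallis in similar simulations (5,000 runs each) rejected 5.6% of the time at 31/31/31 with SD 1:1:2, 7.9% at 45/30/18 with 1:1.5:2, 12.9% at 55/25/13 with 1:2:3, and 2.1% at 55/25/13 with 3:2:1. It is less affected than ANOVA, but not immune.

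**The case against.** The strongest reply is that the large percentages come from chosen inputs. An error rate of two to four times nominal needs marked imbalance, a large SD ratio, and the smallest group being the most variable. The documents establish none of these. With equal groups ANOVA stays at about 5-7%, and with mild imbalance and mild differences in spread it is about 6%. That stands, and it limits what can be claimed.

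Four further points also stand.

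- Preference allocation makes unequal groups plausible, not certain, and the protocol also uses the word randomly. That word comes with no mechanism that would balance the sizes, so it does not remove the exposure.
- An unpaired t test may be the pooled or the Welch version. The plan does not say, so the pooled-variance criticism applies to ANOVA and Tukey, and for the t test the fault is only that the version is open.
- Durations may be skewed and go to the rank tests instead. Which outcomes will pass the normality check is unknown, and no primary endpoint is named. The plan still commits to ANOVA and Tukey for every three-group comparison that passes.
- Confounding is the larger problem. When the operator chooses the method, a difference may reflect the operator or the patient, and no variance correction repairs that.

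The reply does not answer the loss of pairwise power, which needs only unequal spread and arises even with 31 per group.

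**Conclusion.** The point holds as a conditional one. The plan names pooled-variance methods, checks only normality, and fixes no group sizes; if sizes and spreads both differ, the 5% error rate is not held. The illustrative size runs from about 5-7% with equal groups to 18-19% under strong imbalance with the smallest group most variable, and under 2% with those sizes reversed. Separately, unequal spread alone can cut Tukey's power for the two steadier methods from 77% to about 42%.

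A reader might infer that the true error rate of this trial lies between about 2% and 19%. The documents do not support that: they give no SDs and no group sizes, and other inputs give a narrower or a wider range. Nor do they support saying that the groups will be unequal, or that correcting the variance assumption would by itself make a claim of shortest time reliable.

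This is a worthwhile, inexpensive improvement of secondary weight. Confidence is moderate: the mechanism is certain, but its size in this trial is unknown.

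**What to change.** In the SAP (Statistical Analysis) and the matching protocol paragraph, for normally distributed outcomes:

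- replace one-way ANOVA with Welch's ANOVA;
- replace Tukey with Games-Howell comparisons;
- state that the unpaired t test is the unequal-variance (Welch) version;
- apply these without a preliminary test of equal variance.

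The cost is wording only, with no extra patients. If variances are in fact equal and groups are 31 each, simulated power at f=0.33 falls from about 80.4% to 79.7%.

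Two things remain outside this change. The rank tests for non-normal data are left as they are and can also be disturbed by unequal spread, so their results should be read with that in mind. The conflict between preference and random allocation, and the confounding that preference brings, must be resolved separately.
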